7.8 SAFETY ANALYSIS

All safety analyses will be performed on the TS.

Unless stated otherwise, the safety results will be sorted by treatment group.

The safety data for treated subjects who fail to complete the study (dropouts or withdrawals) will be reported as far as their data are available. All withdrawals will be documented and the reason for withdrawal recorded.

7.8.1 Adverse Events

AEs will be coded with the most recent version of MedDRA.

The analyses of AEs will be descriptive in nature and will be based on BI standards as presented in “Analysis and Presentation of Adverse Event Data from Clinical Trials – Display Template” [BI-KMED-BDS-HTG-0041] ([8](#)).

The standard AE analyses will be based on the number of subjects with AEs (and not on the number of AEs).

The analysis of AEs will be based on the concept of treatment emergent AEs. That means that all AEs will be assigned to 'screening', 'on treatment' or 'follow-up' phases as defined in [Section 6.1](#). AEs will be analysed based on actual treatments, as defined in [Table 6.1: 1](#).

Section 1.2.6 of the CTP: The residual effect period (REP) of Spesolimab is 16 weeks.

According to the clinical study protocol, adverse events of special interest (AESI) will be analysed:

Section 5.2.6.1.4 of the CTP: The following are considered as AESIs in this trial:

- *Hepatic injury, as defined by the following alterations of hepatic laboratory parameters:*
 - *an elevation of AST (Aspartate Aminotransferase) and/or ALT (Alanine Aminotransferase) ≥ 3 -fold ULN combined with an elevation of total bilirubin ≥ 2 -fold ULN measured in the same blood sample, or*
 - *ALT, and/or AST elevations ≥ 10 -fold ULN*

These lab findings constitute a hepatic injury alert and the subjects showing these lab abnormalities need to be followed up according to the 'DILI checklist' provided in the ISF. In case of clinical symptoms of hepatic injury (icterus, unexplained encephalopathy, unexplained coagulopathy, right upper quadrant abdominal pain, etc.) without lab results (ALT, AST, total bilirubin) available, the Investigator should make sure that these parameters are analysed, if necessary in an unscheduled blood test. Should the results meet the criteria of hepatic injury alert, the procedures described in the DILI checklist should be followed.

- *Systemic hypersensitivity including infusion reaction and anaphylactic reaction:*
Any suspicion of severe infusion reaction systemic/hypersensitivity reaction and of any potential cases of anaphylaxis should be defined and assessed using the criteria discussed in the statement paper from Sampson HA (Appendix 10.1.3, R11-4890).
- *Severe infections [...]*
- *Opportunistic and mycobacterium tuberculosis infections*
These include pneumocystis jirovecii, BK virus disease including PVAN, CMV, post-transplant lymphoproliferative disorder (EBV), progressive multifocal leucoencephalopathy, bartonellosis (disseminated only), blastomycosis, toxoplasmosis, coccidioidomycosis, histoplasmosis, aspergillosis (invasive only), candidiasis (invasive or pharyngeal), cryptococcosis, other invasive fungi (mucormycosis (zygomycosis, rhizopus, mucor, lichtheimia), scedosporium/pseudallescheria boydii, fusarium), legionellosis, listeria monocytogenes (invasive only), tuberculosis, nocardiosis, non-tuberculous mycobacterium, salmonellosis (invasive only), hepatitis B virus [HBV] reactivation, herpes simplex (invasive only), herpes zoster, strongyloides (hyperinfection syndrome and disseminated forms only), paracoccidioides, penicillium marneffei, sporothrix

schenckii, cryptosporidium species (chronic only), microsporidiosis, leishmaniasis (visceral only), trypanosoma cruzi infection (Chagas' disease) (disseminated only), campylobacteriosis (invasive only), shigellosis (invasive only), vibriosis (invasive due to vibrio vulnificus), hepatitis C virus [HCV] progression (R17- 2617).

According to ICH E3 (9), in addition to Deaths and Serious Adverse Events, 'other significant' AEs need to be listed in the clinical trial report.

The definition of 'other significant' AE to be used in this trial is derived by the sponsor and is based upon that according to ICH E3, and will include AEs reported as non-serious adverse events with 'action taken = Drug Withdrawn' or 'action taken = Drug Reduced'.

An overall summary of adverse events will be presented (including number of subjects with any AE, drug related AEs, serious AEs and drug related serious AEs).

The frequency of subjects with AEs will be summarised by treatment, primary system organ class (SOC) and preferred term (PT). Separate tables will be provided for subjects with SAEs, for subjects with drug-related AEs, patients with investigator-defined AESIs per CTP, and patients with other User-Defined Adverse Event Concepts (UDAEC) (cf. [Table 7.8.1: 1](#) below). In addition, the frequency of subjects with AEs will be summarised by treatment, worst intensity, SOC and PT.

Table 7.8.1: 1 Project MEDDRA search criteria for User Defined Adverse Events Concepts

Important risk	User-defined AE category	
	Label	Description
Infections (serious/severe, opportunistic)	Infections ALL	Combined search strategy based on the individual UDAECs described below; the UDAEC "severe infections (investigator-defined) will be disregarded for this search
	Opportunistic infections	Narrow SMQ "Opportunistic infections"
	Tuberculosis related terms	BlcMQ "Infections": Narrow sub-search 8.2 "Tuberculosis related terms"
	Serious infections	all serious events in SOC "Infections and infestations"
	Severe infections	all events in SOC "Infections and infestations" of at least severe AE grade
	Severe infections (investigator defined)	as per tick box on the eCRF (investigator-defined)

* this is achieved by retrieving all cases found either by running subsearch 1 in narrow scope (BlcMQ search ID 32019093) or subsearch 2 (BlcMQ serach ID 32019094)

Table 7.8.1: 1 Project MEDDRA search criteria for User Defined Adverse Events Concepts - continued

Hypersensitivity	Hypersensitivity ALL	Combined search strategy based on the three individual UDAECs described below
	Anaphylactic reaction	Narrow SMQ “Anaphylactic reaction”
	Angioedema	Narrow SMQ “Angioedema”
	Hypersensitivity	Narrow SMQ “Hypersensitivity”
Malignancies	Malignant tumours	Narrow Sub-SMQ “Malignant tumours” Narrow Sub-SMQ “Haematological malignant tumours” Narrow Sub-SMQ “Non-Haematological malignant tumours”
	Malignant skin tumours	Broad Sub-SMQ “Skin malignant tumours”
	Skin melanomas	HLT Skin melanomas (excl. Ocular)
	Non-melanoma skin cancer (NMSC)	Broad Sub-SMQ “Skin malignant tumours” excluding HLT Skin melanomas (excl. Ocular)
	Malignancies excluding NMSC	Sub-SMQ “Malignant tumours” excluding NMSC, whereas NMSC is defined above
	3-point MACE	BlcMQ 3-MACE with subsearch 1.1 narrow and subsearch 1.2 narrow **
	Torsades de pointes	Broad SMQ “Torsades de pointes/QT prolongation”

* this is achieved by retrieving all cases found either by running subsearch 1 in narrow scope (BlcMQ search ID 32019093) or subsearch 2 (BlcMQ serach ID 32019094)

The system organ classes will be sorted by frequency, PTs will be sorted by frequency (within SOC). The MedDRA version number will be displayed as a footnote in the respective output.

In addition, frequencies of subjects with non-serious AEs that had an incidence of > 5% for at least one treatment will be summarised by treatment, primary SOC and PT.

7.8.2 Laboratory data

The analyses of laboratory data will be descriptive in nature and will be based on BI standards [BI-KMED-BDS-HTG-0042] ([10](#)).

For continuous safety laboratory parameters, normalized values will be derived.

Normalisation means transformation to a standard unit and to a standard reference range. The process of normalisation, handling of repeat values at the same visit for by-visit displays, as well as standard analyses for safety laboratory data are described in the BI guidance for the Display and Analysis of Laboratory Data (10). All analyses considering multiple times of the ULN (as described below) will be based on standardized and not normalized values. For continuous safety laboratory parameters, differences to baseline will be calculated. For all outputs, the last assessment before the first randomized treatment at Day 1 is chosen as the baseline value.

Laboratory data will be analysed qualitatively via comparison of laboratory data to their reference ranges. Only patients with at least one available post-baseline value will be included in the analysis of an individual laboratory parameter. Values outside the reference range as well as values defined as possible clinically significant will be flagged in the data listings.

Descriptive statistics of laboratory values and for the difference from baseline on-treatment (see [Section 6.7](#)) will be based upon standardized values and provided by visit (including summaries of the last value, the minimum value and the maximum value on treatment).

Possibly clinically significant abnormalities will be identified based on BI standard rules which are based on converted lab values and converted reference ranges, i.e. using SI units. These rules will be listed in the SDL appendix of the CTR. Frequency tables will summarize the number of patients with possibly clinically significant abnormalities. If applicable, patients having an abnormal lab value at baseline will be presented separately. A separate listing will present possibly clinically significant abnormal lab values; for each functional lab group all patient's lab values will be listed, if there exists at least one lab value with clinically significant abnormality within the group.

The frequency of patients with AST or ALT elevations $\geq 3\times$ ULN, $\geq 5\times$ ULN, $\geq 10\times$ ULN, and $\geq 20\times$ ULN will be displayed based on standardized laboratory values. To support analyses of liver related adverse drug effects, the frequency of patients with AST and/or ALT $\geq 3\times$ ULN combined with a total bilirubin $\geq 2\times$ ULN in a 30 day period after AST/ALT elevation will be displayed, stratified by alkaline phosphatase $< 2\times$ ULN and $\geq 2\times$ ULN (a patient can potentially be in both alkaline phosphatase strata in case of multiple AST/ALT and bilirubin elevations). The start of the 30 day time span is triggered by each liver enzyme elevation above the defined thresholds. This analysis will be based on standardized laboratory values. A graphical analysis of the ALT and total bilirubin during the on-treatment period will also be performed; the so called eDISH plot. In the graph, for each subject, the peak total bilirubin is presented as a fold increase over the ULN against the peak ALT as a fold increase over the ULN, on a log10 scale. The measurements displayed or total bilirubin and ALT may, or may not, occur on the same date. Two reference lines, 2xULN for total bilirubin and 3xULN for ALT, are drawn onto the graph in order to divide the plane into four quadrants. Normal cases are in the lower left quadrant, potential DILI cases are in the upper right quadrant (Hy's Law quadrant),

while the lower right quadrant is known as the Temple's corollary range (ALT \geq 3xULN and total bilirubin $<$ 2xULN).

Clinically relevant findings in laboratory data will be reported as adverse events if judged clinically relevant by the investigator, and will be analysed as such.

It is the investigator's responsibility to decide whether a lab value is clinically significant abnormal or not (at the RPM/DBLM at the latest).

7.8.3 Vital signs

Descriptive statistics over time including change from baseline will be performed for vital signs (blood pressure, pulse rate and respiratory rate) based on the last value of the subject at that planned time point (or assigned to that planned time point) and including summaries of the minimum value and the maximum value on treatment. In the listing the difference from baseline will also be displayed.

Body temperature will be listed only.

Clinically relevant findings in vital signs will be reported as AEs.

7.8.4 ECG

ECG recordings will be checked by the investigator for pathological results. Clinically relevant abnormal findings for ECG will be listed under 'Relevant Medical History / Baseline Conditions' (if they pre-exist prior to trial inclusion) or will be reported as AEs (if they occurred on treatment), and will be analysed as such.

No separate ECG listing will be provided.

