Based on studies in healthy subjects and patients, no specific drug-related risks are anticipated. Nevertheless, the following safety measures are/will be applied in this trial in order to minimise the risk for the healthy subjects:

- Careful dose selection based on data of the completed studies. In the first dose group of 300 mg SC, the exposure is projected to be similar to the Japanese healthy subjects who were enrolled in trial 1368-0009 and received the same SC dose.
- For the IV dose groups, the administration as 90 minutes infusion allows immediate discontinuation of drug administration should any safety concern arise.
- For both IV and SC dose groups, a time interval of at least two weeks will be maintained between first administration of trial medication in the actual dose level and first administration in the next dose level, which is expected to cover the period of highest risk/peak effect. The next dose will only be given if no safety concerns arise in the previous dose group and if none of the pre-specified trial-specific stopping criteria are met within each IV and SC dose groups.
- Extensive monitoring of 12-lead ECG and vital signs is incorporated, with 12-lead ECG to cover the anticipated period of highest drug exposure. As an additional measure, repeated single 12-lead ECGs are scheduled in the further course of the trial. The rationale for the intensified 12-lead ECG monitoring is not due to expected increased risk of Spesolimab mediated effects on cardiac repolarization, rather, it is been implemented to collect 12-lead ECG data at an early point in clinical development to perform 12-lead ECG interval assessment under drug. In general, for biologics, Time between start of the Q-wave and the end of the T-wave in an electrocardiogram (QT) prolongation is not usually an issue unless there are mechanistic effects with the mAb which can lead indirectly to the 12-lead ECG changes [[R09-2768](#)] but this is not expected to be the case for Spesolimab.
- Extensive safety laboratory testing will be performed.

Proprietary confidential information © 2021 Boehringer Ingelheim International GmbH or one or more of its affiliated companies

- After each dosing, the subjects will stay at the site for at least 48 hours following drug administration.
- During in-house-confinement the subjects will be under close medical observation and thoroughly monitored for both expected and unexpected AEs.

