2.2.2.1 Safety and tolerability

Safety and tolerability of Spesolimab will be assessed based on:

- Safety laboratory parameters
- 12-lead ECG
- Vital signs (blood pressure [BP], pulse rate [PR], respiratory rate [RR], body temperature)
- Immunogenicity (ADA)

Proprietary confidential information © 2021 Boehringer Ingelheim International GmbH or one or more of its affiliated companies

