5.2.4 Electrocardiogram

5.2.4.1 12-lead resting ECG

Recording

Twelve-lead resting ECGs (I, II, III, aVR, aVL, aVF, V1 - V6) will be recorded using a computerised electrocardiograph at the time points given in the [Flow Chart](#).

In order to achieve a stable heart rate at rest and to assure high quality recordings at comparable resting phases, all ECGs will be recorded for a 10-sec duration after the subjects have rested for at least 5minutes in a supine position. The site personnel will be instructed to assure a relaxed and quiet environment so that all subjects are at complete rest during the recordings. ECG assessment will always precede all other trial procedures of the same time point (except blood drawing from an IV cannula which is already in place) to avoid impact of sampling on the ECG quality. Electrode placement will be performed according to the method of Wilson, Goldberger and Einthoven.

At all time points single ECGs will be recorded. All locally printed ECGs will be evaluated by the investigator or a designee. ECGs may be repeated for quality reasons (like alternating current artefacts, muscle movements, electrode dislocation). Additional (unscheduled) ECGs may be collected by the investigator for safety reasons. These ECGs are assigned to the prior scheduled time point. Unscheduled ECGs will not be included into the statistical analysis of interval lengths.

For the inclusion or exclusion (see [section 3.3](#)) of a subject and for the assessment of cardiac safety during the trial, the QT and QTcF values generated by the ECG machines or their manual corrections by the investigators will be used.

Abnormal findings will be reported as AEs (during the trial) or baseline conditions (at screening) if judged clinically relevant by the investigator. Any ECG abnormalities will be monitored carefully and, if necessary, the subject will be removed from the trial and will receive the appropriate medical treatment.

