5.5 APPROPRIATENESS OF MEASUREMENTS

All measurements performed during this trial are standard measurements and will be performed in order to monitor subjects' safety and to determine PK parameters in an appropriate way. The scheduled measurements will allow monitoring of changes in vital signs, standard laboratory values, and 12-lead ECG parameters that might occur as a result of administration of trial medication. The safety assessments are standard, are accepted for evaluation of safety and tolerability, and are widely used in clinical trials. The PK parameters and measurements outlined in [section 5.3](#) are generally used assessments of drug exposure.

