7.3.4 Safety analyses

Safety will be assessed for the endpoints listed in [section 2.1.2](#) and 2.2.2 based on the TS. Safety analyses will be descriptive in nature and will be based on BI standards. No hypothesis testing is planned. Treatments will be compared in a descriptive way. Tabulations of frequencies/proportions will be used for the evaluation of categorical (qualitative) data, and tabulations of descriptive statistics will be used to analyse continuous (quantitative) data.

Measurements (such as vital signs, or laboratory parameters) or AEs will be assigned to treatments (see [section 4.1](#)) based on the concept of treatment emergent AEs. Therefore,

Proprietary confidential information © 2021 Boehringer Ingelheim International GmbH or one or more of its affiliated companies

measurements planned or AEs recorded prior to intake of trial medication will be assigned to 'screening', those between trial medication intake and end of REP will be assigned to the treatment period. Events occurring after the REP but prior to trial termination date will be assigned to 'follow-up'. These assignments including the corresponding time intervals will be defined in detail in the TSAP. Note that AEs occurring after the last per protocol contact but entered before database lock will be reported to Pharmacovigilance only and will not be captured in the trial database.

Additionally, further treatment intervals (called analysing treatments) may be defined in the TSAP in order to provide summary statistics for other than above periods, such as combined treatments, on-treatment totals or periods without treatment effects (such as screening and post-trial intervals).

AEs will be coded using the Medical Dictionary for Regulatory Activities (MedDRA). Frequency, intensity and causal relationship of AEs will be tabulated by treatment, primary system organ class and preferred term. SAEs, AESIs (see [section 5.2.6.1.4](#)) and other significant AEs (according to ICH E3) will be listed separately.

Laboratory data will be compared to their reference ranges. Values outside the reference range will be highlighted in the listings. Additionally, differences from baseline will be evaluated.

Vital signs or other safety-relevant data observed at screening, baseline, during the course of the trial and at the end-of-trial examination will be assessed with regard to possible changes compared to findings before start of treatment.

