8.3.1 Source documents

Source documents provide evidence for the existence of the subject and substantiate the integrity of the data collected. Source documents are filed at the investigator's site.

All data reported in the CRFs must be consistent with the source data or the discrepancies must be explained.

The investigator may need to request previous medical records or transfer records, depending on the trial.

In accordance with regulatory requirements, the investigator should prepare and maintain adequate and accurate source documents and trial records for each trial subject that include all

Proprietary confidential information © 2021 Boehringer Ingelheim International GmbH or one or more of its affiliated companies

observations and other data pertinent to the investigation. Source data as well as reported data should follow the ‘‘ALCOA-C principles’’ and be attributable, legible, contemporaneous, original, accurate and complete. Changes to the data should be traceable (audit trail).

Before providing any copy of subjects’ source documents to the sponsor, the investigator must ensure that all subject identifiers (e.g., subject’s name, initials, address, phone number, and identification card) have properly been removed or redacted to ensure subject confidentiality.

If the subject is not compliant with the protocol, any corrective action (e.g. re-training) must be documented in the subject file.

For the CRF, data must be derived from source documents, for example:

- Subject identification: sex, year of birth (in accordance with local laws and regulations)
- Subject participation in the trial (substance, trial number, subject number, date subject was informed)
- Dates of subject’s visits, including dispensing of trial medication
- Medical history (including trial indication and concomitant diseases, if applicable)
- Medication history
- AEs and outcome events (onset date [mandatory], and end date [if available])
- SAEs (onset date [mandatory], and end date [if available])
- Concomitant therapy (start date, changes)
- Originals or copies of laboratory results and other imaging or testing results, with proper documented medical evaluation (in validated electronic format, if available)
- 12-lead ECG results (original or copies of printouts)
- Completion of subject’s participation in the trial (end date; in case of premature discontinuation, document the reason for it, if known)

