In Section 15.4 and Appendix 16.2 (Listings) of the CTR displays, the screening and follow-up period will be included and no totals will be provided.

Tables of vital signs and laboratory values will present results for the above mentioned on treatment phase.

For detailed information on the handling of the treatments refer to Technical TSAP ADS (analysis data set) plan and Analysis Data Reviewers guide.

6.2 **IMPORTANT PROTOCOL DEVIATIONS**

Data discrepancies and deviations from the CTP will be identified for all treated subjects.

Consistency check listings (for identification of deviations of time windows) and a list of protocol deviations (e.g. deviations in drug administration, in blood sampling times, etc.) will be provided to be discussed at the Report Planning Meeting and database lock meeting (RPM/DBLM). At this meeting, all manual deviations identified at the sites by the CRAs and deviations too complex to program will be reviewed by the trial team to decide which are considered important. For definition of important protocol deviations (iPD), and for the process of identification of these, refer to the Boehringer Ingelheim (BI) SOP "Identify and Manage Important Protocol Deviations (iPD)" (2).

If any iPDs are identified, they are to be summarised into categories and will be captured in the RPM/DBLM minutes via an accompanying Excel spreadsheet.

Categories which are considered to be iPDs in this trial were defined in the integrated quality and risk management plan (IQRMP) prior to trial initiation. The IPD list was transferred into the IPD specification file (due to changes in the SOP) (3). Within this transfer some minor adaptations were done to comply with new naming conventions and categorisations. IPDs will be identified no later than in the Report Planning Meeting and the IPD categories will be updated as needed. The decision on exclusion of subjects from analysis sets will be made after discussion of exceptional cases and implications for analyses.

The iPDs will be summarised and listed.

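### SAP 7.8.4 drops the ECG interval analysis that the protocol foresees, and SAP Section 4 does not declare the change

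*SAP*

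**What the plan says.** **Protocol.** Section 1.4 states that the intensified 12-lead ECGs are not there because an effect on repolarisation is expected. Their purpose is "to collect 12-lead ECG data at an early point in clinical development to perform 12-lead ECG interval assessment under drug". Section 5.2.4.1 names the machine-generated or manually corrected QT and QTcF as the values for assessing cardiac safety, and adds: "Unscheduled ECGs will not be included into the statistical analysis of interval lengths". Section 2.2.2.1 opens with "Safety and tolerability of Spesolimab will be assessed based on" and has 12-lead ECG as its second item. Section 5.5 says: "The scheduled measurements will allow monitoring of changes in vital signs, standard laboratory values, and 12-lead ECG parameters". Section 7.3.4 covers the endpoints of section 2.2.2 and states that "tabulations of descriptive statistics will be used to analyse continuous (quantitative) data".

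**SAP.** Section 5.2.2 repeats the safety list, including 12-lead ECG. Section 7.8.4 has the investigator check the recordings and sends clinically relevant abnormalities to medical history or to adverse events. It then says: "No separate ECG listing will be provided". Section 6.1 announces summary tables for two kinds of measurement only: "Tables of vital signs and laboratory values will present results for the above mentioned on treatment phase". Section 4 says that all protocol analyses will be carried out and lists three changes: where the categories of important protocol deviations are kept, the definition of severe infections, and the removal of the emesis criterion.

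**The concern.** The protocol gives a purpose for the ECG schedule, and the SAP contains no analysis that serves it. If the SAP is followed as written, the report will hold no measured QT or QTcF result for any dose group, neither summarised nor listed. A shift in the interval that no investigator thought clinically relevant would appear nowhere.

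The change is also undeclared. A reader who relies on Section 4 would believe that the interval analysis had been kept.

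**Working it through.** The plan states no figure on this point, so the check compares passages and then counts the data affected.

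**1. Does the protocol foresee an interval analysis?**
- Section 1.4 gives interval assessment under drug as the reason for the schedule.
- Section 5.2.4.1 excludes unscheduled ECGs from a statistical analysis of interval lengths. That rule has no function unless such an analysis exists.
- Section 7.3.4 does not name ECG. It does apply descriptive tabulation of continuous data to the section 2.2.2 endpoints, and 12-lead ECG is one of them. This step is an inference; the two above are explicit.

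**2. Does the SAP plan it?**
- Section 7.8.4 has no descriptive statistics, no change from baseline and no listing for ECG intervals. Section 7.8.3, by contrast, gives blood pressure, pulse rate and respiratory rate all three.
- The general rule in SAP Section 7 that individual values are listed does not help, because 7.8.4 specifically rules out an ECG listing.
- The QT-prolongation search in SAP Table 7.8.1: 1 works on coded adverse event terms, not on measured intervals.

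**3. Is the omission declared?** No. None of the three changes in SAP Section 4 concerns ECG.

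**4. How much data is affected?** The inputs are the ECG column of the two protocol flow charts, which is the same for IV and SC, and 50 planned subjects (5 groups of 10).

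| Item | Per subject | In 50 subjects |
|---|---|---|
| Pre-dose, Day 1 | 1 | 50 |
| Post-dose: 0:30, 1:30, 2:00, 6:00, 12:00, 24:00, 48:00, Days 8, 22, 29, 176 | 11 | 11 × 50 = 550 |
| On-study total | 12 | 12 × 50 = 600 |
| Of these, pre-dose to 48 h | 1 + 7 = 8 | 8 × 50 = 400 |

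The screening ECG is left out because it serves eligibility.

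The residual effect period is 16 weeks (Protocol 1.2.6), which is 16 × 7 = 112 days after dosing, or Day 113. Day 176 lies beyond it. So 10 × 50 = 500 post-dose ECGs fall in the on-treatment phase and 1 × 50 = 50 fall after it.

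Safety is analysed in the treated set, which can reach 60 with replacements. If all 60 had every ECG, the total would be 12 × 60 = 720. Replaced subjects leave early, so the true number would be lower.

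**The case against.** - **The adverse event route is the protocol's own.** Protocol 5.2.4.1 says that abnormal ECG findings are reported as adverse events or baseline conditions when judged relevant, and SAP 7.8.4 follows this closely. That is correct, but the same protocol section also refers to a statistical analysis of interval lengths. The two stand side by side, and the SAP keeps only one.
- **The protocol never specifies an interval table.** Section 7.3.4 gives vital signs and laboratory parameters as its examples, and section 5.5 says only what the schedule makes possible. This stands as a limit on detail. It does not remove the explicit statements in 1.4 and 5.2.4.1.
- **Measured QTc is used during the trial.** Section 5.2.4.1 uses the values for cardiac safety, and section 3.3.4.3 has a numerical QTc criterion for stopping dose escalation. So the values are looked at subject by subject, but nothing from that use reaches the report.
- **The rationale in 1.4 may be carried-over text.** It speaks of an early point in development, yet section 1.2.5 counts six completed phase I and four completed phase II trials. This is plausible. Section 4 is then where it should be said, as was done for the emesis criterion.
- **Parts of the SAP are not visible.** An ECG display in the hidden sections cannot be fully excluded. It is unlikely, because the dedicated ECG section is complete and points to none, while SAP Section 7 refers to 7.6 for PK analyses and to 9.1 for the interim analysis.
- **The yield is small.** This stands, and it bears on the weight of the point rather than on whether it is right.

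**Conclusion.** The point holds. SAP 7.8.4 contradicts the purpose and the data rule that the protocol sets for ECGs, and the completeness statement in SAP Section 4 is inaccurate as written. In 50 subjects, 600 on-study ECGs, 550 of them post-dose, have no planned quantitative output.

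This should be corrected, but it does not threaten the trial's main results. The primary endpoints (AUC to infinity and Cmax) and the secondary endpoints (adverse events) do not depend on it, pulse rate is summarised under SAP 7.8.3, and the protocol expects no QT prolongation. An interval summary would describe the data and could not establish or exclude an effect.

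The conclusion assumes that no ECG display sits in the SAP sections that cannot be seen. The counts assume 50 subjects with complete schedules.

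**What to change.** In SAP 7.8.4, replace the sentence that rules out a listing with the following plan:
- Descriptive statistics of QT and QTcF, and of their change from baseline, by dose group and planned time point in the treated set.
- Baseline as defined in SAP 6.7, which is the Day 1 pre-dose value when it is available.
- Scheduled ECGs only, in line with Protocol 5.2.4.1.
- A statement of how the Day 176 ECG is shown, since it falls after the on-treatment phase.
- A listing of individual values.

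The cost is SAP wording, a few standard tables and one listing. No new measurement is needed. The documents do not say whether QT and QTcF are already in the eCRF. If they are not, up to 2 × 600 = 1,200 values for 50 subjects (2 × 720 = 1,440 at the 60-subject maximum) must be entered from the printouts that Protocol 8.3.1 already names as source documents.

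If the sponsor decides against the analysis, SAP Section 4 should declare the removal and give the reason. That costs about one sentence and makes Section 4 accurate, but the interval result is then still not reported.
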